Tumor Ablation in Metastatic Sarcoma Stable on Chemotherapy

**Washington University School of Medicine
Division of Oncology
[name]
[name]**

**Protocol#: 201309108
Version Date: 05/17/17**

Principal Investigator: [name] [name]., Ph.D.
[contact]
E-mail: [contact]

Sub-Investigators	Modality
[name].	Medical Oncology
[name].	Radiology
[name].	Biostatistics

Clinical Trials.gov# NCT01986829

CONFIDENTIAL

The information contained in this document is regarded as confidential and, except to the extent necessary to obtain informed consent, may not be disclosed to another party unless law or regulations require such disclosure. Persons to whom the information is disclosed must be informed that the information is confidential and may not be further disclosed by them

Tumor Ablation in Metastatic Sarcoma Stable on Chemotherapy

Protocol Revision History

Initial Approval Version	09/09/2013
Amendment #1 Version	10/06/2014
Amendment #2 Version	12/20/2016
Amendment #3 Version	05/17/2017

Tumor Ablation in Metastatic Sarcoma Stable on Chemotherapy

SCHEMA

Eligible Patients

Patients with high-grade metastatic sarcoma stable on chemotherapy for 6-12 cycles with 10 or fewer metastatic lesions which are amenable to ablation and which are measurable by CT, PET/CT, or MRI

Treatment Plan

Chemotherapy stopped at initiation of ablation therapy. All ablation therapy completed within 3 weeks with CT/PET every 9 weeks for the first year, every 12 weeks for the second year, and then every 6 months until radiographic progression or 5 years

Glossary of Abbreviations

AE	Adverse event
ALT (SGPT)	Alanine transaminase (serum glutamate pyruvic transaminase)
ANC	Absolute neutrophil count
AST (SGOT)	Aspartate transaminase (serum glutamic oxaloacetic transaminase)
BPI	Brief Pain Inventory
CBC	Complete blood count
CFR	Code of Federal Regulations
CMP	Complete metabolic panel
CR	Complete response
CRF	Case report form
CT	Computed tomography
CTCAE	Common Terminology Criteria for Adverse Events
CTEP	Cancer Therapy Evaluation Program
DOB	Date of birth
DSM	Data and Safety Monitoring
ECOG	Eastern Cooperative Oncology Group
FDA	Food and Drug Administration
HRPO	Human Research Protection Office (IRB)
INR	International normalized ratio
IR	Interventional radiology
IRB	Institutional Review Board
IULN	Institutional upper limit of normal
MRI	Magnetic resonance imaging
NCI	National Cancer Institute
NIH	National Institutes of Health

1.0 BACKGROUND AND RATIONALE

1.1 Study Disease

Sarcomas encompass a group of an estimated 70 different histologic subtypes with varying biology (1). There are approximately 13,000 new cases of sarcoma per year in the United States, accounting for about 1% of adult malignancies (2). Prognosis is poor for patients with metastatic disease, with only a median survival of 12 months. Given the biological diversity of these tumors, a single drug therapy is not likely to be successful across all subtypes. As such, novel and multidisciplinary approaches will likely be needed to improve survival.

1.2 Ablation for Sarcoma

Cytotoxic chemotherapy is the mainstay of therapy for metastatic sarcoma. This alone, however, is very unlikely to result in a durable remission or cure. There is data demonstrating increased survival following surgical removal of pulmonary metastases in the setting of osteosarcoma. The combination of chemotherapy with resection of pulmonary metastases has been shown to increase the 3-year survival in metastatic osteosarcoma from approximately 5% to 65% (3). An alternative procedural approach to treating metastatic cancer includes ablation therapy. We hypothesize that we can use ablation therapy as a form of maintenance therapy in this patient population.

There is retrospective data that radiofrequency ablation is safe in sarcoma patients with lung metastases with a 3-year survival of 65%, similar to what is quoted in surgical studies (4). Given these data, we propose this single arm prospective phase II trial of ablation therapy in metastatic sarcoma patients that have less than 10 lesions that are stable on chemotherapy. These patients must be stable on 6-12 cycles of either cytotoxic or biologic chemotherapy as this is the natural stopping point for Adriamycin-based chemotherapy, which is the standard treatment in soft tissue sarcoma. Ablation therapy will then substitute as a form of maintenance therapy.

Tumor ablation will include radiofrequency ablation, cryoablation, or microwave ablation, and will include vertebral augmentation/cementoplasty of metastases with pathologic fracture or impending risk of fracture in the axial-loading bones including vertebral bodies and pelvis. These techniques are thought to be equivalent and the choice of which type of ablation to use is based on the performing radiologist and the site of metastasis. Others have validated the use of progression-free rate (PFR) as a surrogate for activity in phase II sarcoma studies (5). We hypothesize that there will be at least a 40% 3-month PFR indicating a significant response to ablation therapy.

2.0 OBJECTIVES

2.1 Primary Objectives

To determine the progression-free rate at 3 months in patients with metastatic sarcoma stable on chemotherapy whose lesions have undergone ablation. PFR is defined as the percentage of patients with no progression (local recurrence of an ablated lesion or the appearance of a new lesion) at 3 months after ablation.

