5.6 Evaluability

All patients who undergo ablation are evaluable for toxicity. Patients are evaluated from date of first procedure and for 30 days thereafter.

All patients who undergo ablation are evaluable for disease response provided they have had at least one disease assessment.

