5.9 Duration of Therapy

Tumor ablation is a one-time procedure. If at any time prior to or during ablation, the constraints of this protocol are considered to be detrimental to the patient's health and/or the patient no longer wishes to proceed with ablation, this treatment should be discontinued and the reason(s) for discontinuation documented in the case report forms.

Because the ablation procedures are intended to replace maintenance chemotherapy, chemotherapy should not resume following ablation therapy. If the treating physician feels it is warranted (i.e., the patient develops a lesion that is not amenable to ablation), then the patient will be considered to have progressed and will be taken off trial and replaced.

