9.0 MEASUREMENT OF EFFECT

9.1 Antitumor Effect – Solid Tumors

There will be another PET/CT at 42 +/- 3 days following the last procedure (approximately 6 weeks post-procedure) and one every 9 weeks thereafter until progression of disease. All imaging is standard of care.

For the purposes of this study, patients should be re-evaluated for response every 9 weeks. In addition to a baseline scan, confirmatory scans should also be obtained 4 weeks (not less than 4) weeks following initial documentation of objective response.

Response and progression will be evaluated in this study using the new international criteria proposed by the revised Response Evaluation Criteria in Solid Tumors (RECIST) guideline (version 1.1) [Eur J Ca 45:228-247, 2009]. Changes in the largest diameter (unidimensional measurement) of the tumor lesions and the shortest diameter in the case of malignant lymph nodes are used in the RECIST criteria.

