11.0 STATISTICAL CONSIDERATIONS

11.1 Power

Our power analysis is based on the following hypotheses. The null hypothesis assumes that the 3-month progression-free survival (PFS) for treatment with ablation therapy is

overall 20% for patients with metastatic sarcoma. We hypothesize in the alternative hypothesis that the 3-month PFS will be at least 40% with ablation therapy. This is based on data from a clinical trials database used to provide reference values for conducting phase II studies in sarcoma with PFR as the principal endpoint (5). An enrollment of 36 patients can achieve at least 80% power to conclude that the alternative hypothesis is true based on a two-sided test of one-sample proportion at a significance level of 0.05.

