11.2 Data Analysis

Possible covariates in the analysis include sex, age, number of lesions and total diameter of all ablated lesions. Descriptive statistics (mean, median, range and standard deviation) will be provided for continuous variables and frequencies will be tabulated for categorical variables for the patients. Kaplan-Meier survival estimates will be obtained for 3-month PFS for patients with ablation therapy. For categorical covariates such as sex, number of lesions (<5 vs. ≥5) and total diameter of all ablated lesions (10cm vs. ≥10cm), if there are sufficient number of patients in each stratum, Kaplan-Meier survival curves will be plotted for each stratum and log-rank test will be performed to test if 3-month PFS is significantly different across strata. Overall survival will be analyzed with the same strategy as for 3-month PFS.

To determine whether or not there is an improvement in quality of life (QOL), since the variables related to QOL are in ordinal scale and will be measured at baseline, one day post ablation, one month post ablation and at time of disease progression, the GEE analysis implemented in SAS PROC GENMOD will be used to take into account the correlation of repeated measures from the same subject. Contrast statements will be used to compare mean QOL scores between any two times. The same analysis strategy will be performed to determine if BPI changes over time.

All analyses will be two-sided at a significance level of 0.05 and will be performed with statistical software SAS 9.3.

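### The written primary endpoint (3-month PFR) leaves out death, the 3-month PFS that is tested is never defined, and no rule says whether the lesion-level definition or RECIST 1.1 governs

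*Combined protocol and SAP*

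**What the plan says.** **Definition.** Section 2.1 (Primary Objectives) states: "PFR is defined as the percentage of patients with no progression (local recurrence of an ablated lesion or the appearance of a new lesion", with status taken at 3 months after ablation. Section 9.4.5 repeats this. The overall survival definition beside it names death; this one does not.

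**Hypotheses and analysis.** Section 1.2 sets the target as a PFR: "We hypothesize that there will be at least a 40% 3-month PFR indicating a significant response to ablation therapy". Section 11.1 sets the same 40% as a PFS: "We hypothesize in the alternative hypothesis that the 3-month PFS will be at least 40% with ablation therapy". Its null is 20%, the rates are attributed to reference values for PFR, and N=36 comes from a two-sided one-sample proportion test. Section 11.2 then says "Kaplan-Meier survival estimates will be obtained for 3-month PFS for patients with ablation therapy". PFS is spelled out in the glossary and defined nowhere. Death appears in 5.10 and in the 7.0 calendar footnote only as a point where follow-up or imaging stops.

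**Who is counted.** Section 5.6: "All patients who undergo ablation are evaluable for disease response provided they have had at least one disease assessment". Section 5.9, on a patient for whom chemotherapy is judged warranted after ablation: "then the patient will be considered to have progressed and will be taken off trial and replaced".

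**A second progression standard.** Section 9.1: "Response and progression will be evaluated in this study using the new international criteria", namely RECIST 1.1. Section 9.4.1 requires a rise of at least 20% and 5 mm in the target-lesion sum. Section 9.4.2 says non-target progression must reflect overall disease change, not growth of one lesion. New lesions count under both standards.

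**The concern.** A single-arm trial compared with a fixed 20% depends entirely on how each patient is scored at 3 months. Here the scoring of a death is left to whoever runs the analysis. The written definition makes a death without recorded progression a non-event. The label PFS would ordinarily make it a failure. A Kaplan-Meier analysis using only the listed events would censor it. Section 5.6 would remove the patient if death came before any post-ablation scan. Scoring such a death as progression-free, censoring it or removing it raises the reported rate above what a death-as-failure rule would give.

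The RECIST overlap matters for a different reason. Regrowth of a single ablated lesion is the failure this treatment is most directly meant to prevent. It is a failure under 2.1 but may not be progressive disease under 9.4.1 or 9.4.2.

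**Working it through.** **1. The plan's own figure.** Inputs from 11.1: null 0.20, alternative 0.40, two-sided 0.05, 80% power.

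n = [(1.960·√(0.20·0.80) + 0.842·√(0.40·0.60)) / 0.20]² = 35.8, so 36. Power at 36 is 80.2%. The sample size reproduces; the defect is in the endpoint, not the arithmetic.

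The cut-off is not stated. The test that reproduces N=36 rejects at 12/36: z = (0.3333 − 0.20)/√(0.16/36) = 2.00, p = 0.046. An exact binomial test needs 13/36. At a true 20%, P(X≥12) = 4.2% and P(X≥13) = 1.8%.

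**2. Deaths before the first scan, dropped under 5.6.** The documents give no early-death rate for these patients. Two assumed bounds, both with exponential survival, 6 weeks = 1.38 months and no progression recorded before death:
- Low, from the 65% 3-year survival quoted in 1.2: 1 − 0.65^(1.38/36) = 1.6%, or 0.59 of 36 patients.
- High, from the 12-month median in 1.1 ("Prognosis is poor for patients with metastatic disease, with only a median survival of 12 months"): 1 − 0.5^(1.38/12) = 7.7%, or 2.76 of 36.

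No passage replaces patients who die. Dropping them therefore shrinks the denominator and leaves the number of successes unchanged. Let K ~ Binomial(36, q) be the deaths, 36 − K the patients analysed, and 0.20/(1 − q) the success probability among them. The cut-off is recomputed for each denominator (score test: 12 for n = 33 to 36, 11 for n = 29 to 32).

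| Cut-off | No deaths dropped | q = 1.6% | q = 7.7% |
|---|---|---|---|
| Score test | 4.2% | 4.3% | 5.3% |
| Exact | 1.8% | 1.9% | 2.8% |

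The effect is small because the score cut-off falls only once four or more patients have been dropped.

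**3. Deaths after a clean first scan, read literally.** These patients are evaluable under 5.6, so the definition in 2.1 can operate on them. Each such death scored as progression-free adds 1/36 = 2.8 percentage points. With 11 patients alive and progression-free plus one such death, the literal score is 12/36 (p = 0.046). With death as failure it is 11/36: z = (0.3056 − 0.20)/0.0667 = 1.58, p = 0.11.

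Purely as illustration, if 1% or 3% of patients had such a death, P(X≥12) at a true 20% becomes P(X≥12 | 36, 0.21) = 5.9% or P(X≥12 | 36, 0.23) = 10.4%. For the exact cut-off, P(X≥13) becomes 2.7% or 5.2%. Nothing in the documents supports a particular rate.

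**4. Lesion rule against RECIST.** Hypothetical case: five 30 mm target lesions, no shrinkage, one recurring to 40 mm. The sum goes from 150 to 160 mm, a rise of 10/150 = 6.7%. That exceeds 5 mm but is well under 20%, so it is not progression on the sum. Under 2.1 it is a failure. Section 9.2 requires the status of each non-target lesion to be noted, so the data for a lesion-level rule may exist. The direction of effect across patients is not shown.

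**5. When 3 months is assessed.** Three months is about 13.0 weeks. Section 7.0 counts 6 weeks from the first procedure, 9.1 counts 42 ± 3 days from the last, and 5.10 lists only 9-weekly scans. Six plus nine weeks is week 15; 9-weekly scans alone fall at weeks 9 and 18. No section schedules a scan at 3 months or says which scan decides.

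**The case against.** The strongest reply is that PFS conventionally counts death, and both the hypotheses and the analysis use that term. On this view the plan has a missing definition, not a rule that rewards death. That is fair as far as it goes: no section actually says that death is a success, a failure or censored, and part of the problem is silence. But the only written definition of the primary endpoint is a closed list without death, and convention cannot override explicit text for a primary endpoint.

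A reader might infer that early deaths would badly inflate the false-positive rate. The documents do not support that. Deaths before the first scan are arguably not evaluable under 5.6, so they would be dropped rather than scored as successes, and the effect of dropping them is small. The 12-month median is also likely pessimistic for patients who have had no progression through 6 to 12 cycles, have ECOG 0 to 2 and have at most 10 treatable lesions.

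A reader might also infer from 5.9 that replaced patients are removed as failures. The section does not say so. It deems them progressed, its example is a newly developed lesion (already a failure under 2.1), and 5.6 keeps assessed patients evaluable. What remains is a risk from silence, since no passage says they stay in the primary analysis. One patient could matter only at the boundary: 12/36 gives p = 0.046, while 12/37 gives z = 1.89, p = 0.059.

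On RECIST, 9.4.5 is the trial-specific definition within the same chapter and could be taken to govern. No sentence says that it does.

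**Conclusion.** The concern holds, and the plan should be corrected before analysis. Followed literally, the stated rules can misclassify patients on the primary endpoint: a death without recorded progression counts as progression-free, a death before the first assessment may leave the analysis, and a single local recurrence may or may not count, depending on the section used.

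The demonstrated size is modest. Dropping deaths before the first scan raises the false-positive rate by about 0.1 to 1.0 percentage points on either cut-off, given the assumed 1.6% to 7.7% death range and no replacement of deaths. The literal reading has a larger effect per death, but its total depends on an unknown number of deaths after a clean first scan. The 12/36 cut-off is inferred from the formula that reproduces N=36. Replacement is a risk from silence only, and no direction is claimed for the RECIST overlap.

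**What to change.** - Use one definition in 2.1, 9.4.5, 11.1 and 11.2: failure is local recurrence of any ablated lesion, a new lesion, or death from any cause by 3 months.
- State that this lesion-level rule governs the primary endpoint and that the RECIST sum and non-target rules are descriptive.
- Make the denominator all patients who start ablation. Patients considered progressed under 5.9 by 3 months stay in as failures even if further patients are enrolled.
- Confirm whether the 20% and 40% reference values count death in the same way, and restate them if not. The documents do not say, and the endpoint must match its benchmark.
- Reconcile the imaging schedules in 5.10, 7.0 and 9.1. State whether 3 months runs from the first or last procedure, and name the existing scan that determines 3-month status and how a missing scan is scored.

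**Cost.** Wording only, with a slightly lower reported rate. Two consequences should be accepted knowingly. If missing status is scored as failure, power at 12/36 falls from 84% (exact, true 40%) to 77% with 5% missing (true rate 0.40 × 0.95 = 0.38) and to 69% with 10% missing (0.36). If a scan near week 15 is named, the 3-month benchmarks do not transfer directly: under an assumed constant hazard, 40% at 13.04 weeks becomes 0.40^(15/13.04) = 34.9%, with 64% power against an unchanged 20%.

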2.2 Secondary Objectives

1. To determine the rate of overall survival of patients with metastatic sarcoma stable on chemotherapy whose lesions have undergone ablation. Overall survival is defined as the time from diagnosis of metastatic disease to the time of death.
2. To determine the effects of ablation on quality of life (QOL) as measured with the FACT-G7 validated survey.
3. To determine the effects of ablation on pain as measured by the Brief Pain Inventory (BPI)-Short form, a validated scale for assessment of pain.

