3.0 PATIENT SELECTION

3.1 Inclusion Criteria

1. Histologically or cytologically confirmed high-grade metastatic sarcoma that has been stable on 6-12 cycles of one chemotherapeutic regimen (cytotoxic or biologic) although a change in chemotherapy is allowed if it is a result of toxicity/tolerability rather than progression. A patient must not have evidence of progression at any time while on chemotherapy in order to be eligible for this trial.
2. Measurable disease defined as lesions that can be accurately measured in at least one dimension (longest diameter to be recorded) as ≥ 10 mm with CT scan, PET CT, or MRI exam.
3. At least 18 years of age.
4. ECOG performance status ≤ 2 (Karnofsky $\geq 60\%$, see Appendix A)
5. Normal bone marrow and organ function as defined below:
 - a. Leukocytes $\geq 3,000/\text{mcl}$
 - b. Absolute neutrophil count $\geq 1,500/\text{mcl}$
 - c. Platelets $\geq 100,000/\text{mcl}$
 - d. Total bilirubin $\leq 1.5 \times \text{IULN}$ or $3 \times \text{IULN}$ with normal ALT and AST in patients with Gilbert's disease
 - e. $\text{AST(SGOT)/ALT(SGPT)} \leq 3.0 \times \text{IULN}$

- f. Creatinine less than the institutional upper limit of normal
OR
Creatinine clearance ≥ 50 mL/min/1.73 m²
 - g. INR < 1.5 or patient off Coumadin at the time of ablation
6. No more than 10 treatable lesions as evaluated by an experienced interventional oncologic radiologist for eligibility and lesion accessibility as the ablation of more than 10 lesions becomes technically infeasible. These lesions must be treated in a two- to three-week time period from initial interventional radiology evaluation. Lung and liver lesions can range from 1 cm to 7 cm for a single lesion and no greater than 5 cm for multiple lesions. There are no size criteria for the osseous lesions.
 7. The lesions will be amenable to a safe, ultrasound/computed tomographic/fluoroscopic guided percutaneous approach. The targeted metastases must be sufficiently separateable from the central nervous system, major peripheral motor nerves, bowel, and bladder. All lesions must be amenable to treatment.
 8. If patients have received radiation therapy, there must be a one-month washout period.

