9.4.5 Other Definitions

Progression-free rate: PFR is defined as the percentage of patients with no progression (local recurrence of an ablated lesion or the appearance of a new lesion) at 3 months after ablation.

Overall survival: OS is defined as the time from diagnosis of metastatic disease to the time of death.

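### Overall survival is timed from metastatic diagnosis, so it includes survival that eligibility guarantees and does not measure survival after ablation

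*Combined protocol and SAP*

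**What the plan says.** The first secondary objective in Section 2.2 is "To determine the rate of overall survival of patients with metastatic sarcoma stable on chemotherapy whose lesions have undergone ablation". The next sentence sets the clock: "Overall survival is defined as the time from diagnosis of metastatic disease to the time of death". Section 9.4.5 gives the same origin: "OS is defined as the time from diagnosis of metastatic disease to the time of death".

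Section 3.1 requires metastatic sarcoma that has been stable through 6-12 cycles, and adds: "A patient must not have evidence of progression at any time while on chemotherapy in order to be eligible for this trial". The Schema places ablation after that: "Chemotherapy stopped at initiation of ablation therapy".

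On analysis, Section 11.2 says only: "Overall survival will be analyzed with the same strategy as for 3-month PFS". For PFS, that strategy is Kaplan-Meier estimation, with curves by stratum and log-rank tests where strata are large enough. No section provides for delayed entry, a landmark, or a second OS measure timed from registration or ablation. The primary progression-free rate, by contrast, is counted from ablation (Sections 2.1 and 9.4.5).

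**The concern.** The OS clock starts before patients can qualify for the analysis. Someone who died or progressed during chemotherapy cannot be enrolled, and someone who died before the procedure is not among the ablated. Each patient's OS is therefore a stretch in which death was impossible by design, plus the survival that followed ablation.

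The result answers neither natural question. It is not survival after the intervention, because it adds time accrued before the intervention. It is not survival from metastatic diagnosis, because early deaths are excluded and the risk sets are not adjusted for that. A reader who takes it as either will see survival overstated.

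The planned log-rank tests have a related problem. If strata differ in how long patients were on chemotherapy before ablation, that difference enters the OS comparison alongside any difference in survival afterwards.

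**Working it through.** **The plan's own figures.** The documents give no target, event count or power for OS. The only design figure is the 36 patients in Section 11.1 for the primary endpoint (20% versus 40%, two-sided 0.05, at least 80% power). It reproduces by the normal approximation: n = ((1.96 × √0.16 + 0.842 × √0.24) / 0.2)² = 35.78, rounded up to 36, with power 80.2%. OS plays no part in it.

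**Inputs.** Cycles before entry: 6 to 12 (Section 3.1). Assumptions, because the documents are silent: cycles of 2, 3 or 4 weeks; chemotherapy starts at metastatic diagnosis; no gap between chemotherapy and ablation; full cycles counted. One month is 30.4375 days.

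**Step 1: lead-in.** d = cycles × weeks per cycle × 7 / 30.4375.

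| Cycle length | 6 cycles | 12 cycles |
|---|---|---|
| 2 weeks | 2.76 months | 5.52 months |
| 3 weeks | 4.14 months | 8.28 months |
| 4 weeks | 5.52 months | 11.04 months |

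**Step 2: effect on the median.** For each patient, T(diagnosis) = d + T(ablation). If every d lies between a and b, then median T(ablation) + a ≤ median T(diagnosis) ≤ median T(ablation) + b. This holds for any survival distribution. The excess is therefore 4.1 to 8.3 months with 3-week cycles, 2.8 to 5.5 with 2-week cycles and 5.5 to 11.0 with 4-week cycles.

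As a check, patients were spread evenly over 6 to 12 cycles. Post-ablation survival was Weibull with shape 0.7, 1.0 or 1.5 and median 6, 12 or 24 months. The shift in the median was 6.23 to 6.33 months in all nine 3-week cases, 4.15 to 4.20 with 2-week cycles and 8.32 to 8.50 with 4-week cycles.

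**Step 3: share of the reported median that is lead-in.** Share = d / (d + post-ablation median), 3-week cycles, with the post-ablation median assumed:

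| Post-ablation median | 6 cycles | 12 cycles |
|---|---|---|
| 6 months | 4.14/10.14 = 41% | 8.28/14.28 = 58% |
| 12 months | 4.14/16.14 = 26% | 8.28/20.28 = 41% |
| 24 months | 4.14/28.14 = 15% | 8.28/32.28 = 26% |

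**Step 4: effect on a survival rate.** Take exponential survival with a 12-month median after ablation. The 12-month rate is 50.0% from ablation. For the same deaths timed from diagnosis it is exp(−ln 2 × (12 − d)/12), which is 63.5% with d = 4.14 and 80.7% with d = 8.28.

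**Step 5: early deaths that cannot be seen.** Apply the 12-month median in Section 1.1 as an exponential from metastatic diagnosis. Then 1 − exp(−ln 2 × d/12) gives 21% of unselected patients dead by 4.14 months and 38% by 8.28 months. None of them could enter this trial.

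**The case against.** The strongest reply is that the plan states its OS origin openly and consistently. Objectives 2 and 3 in Section 2.2 ask for effects of ablation, but the OS objective asks only for the survival of a described group. There is no OS comparator, threshold or power claim. This stands in part: no passage contradicts another, and no planned comparison with an outside value is spoiled. It does not rescue the estimate. Plain Kaplan-Meier from diagnosis is also biased for survival from diagnosis, so it fails on the plan's own stated origin.

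The size rests on assumptions about cycle length, the start of chemotherapy and post-ablation survival. That is fair. The upper figures are not upper limits either, because any gap before chemotherapy or ablation adds to them. The direction needs none of these assumptions.

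The from-diagnosis curve could be kept with delayed entry. In a simulation (36 patients, 4,000 runs, uniform 6-12 three-week cycles, exponential survival with a 12-month median after ablation), the delayed-entry median was 16.2 months. Its target is 4.14 + 12 = 16.14, so it is well centred. Its 95% range was 8.6 to 22.9 months, against 6.9 to 17.6 when timing starts at ablation, so the loss of precision is moderate. The median risk set at the first death was 14 of 36, and it was 9 or fewer in 26% of runs. More importantly, the method estimates survival conditional on reaching the earliest entry time, which is still not survival after ablation.

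Two smaller points also stand. Section 5.6 ("Patients are evaluated from date of first procedure and for 30 days thereafter") concerns toxicity, so it shows that the first-procedure date is in use but sets no precedent for OS. And OS is not purely descriptive, because log-rank tests are planned.

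**Conclusion.** The concern holds. Followed as written, the plan builds eligibility-guaranteed survival into the OS curve. That conclusion and its direction rest on Sections 2.2, 3.1, 9.4.5, 11.2 and the Schema alone.

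The amount is illustrative: 4.1 to 8.3 months on the median with 3-week cycles, and 2.8 to 11.0 months across 2- to 4-week cycles, if chemotherapy starts at diagnosis and ablation follows at once.

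If the reference in Section 11.2 to the 3-month strategy were read as reporting OS at 3 months, the result would be 100% by eligibility once cycles last 13.04/6 = 2.17 weeks or more. The more natural reading is that it refers to the Kaplan-Meier and log-rank methods.

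The consequence is confined to a secondary endpoint. It should be corrected, but it does not touch the primary analysis.

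**What to change.** In Sections 2.2, 9.4.5 and 11.2, define OS as time from the date of first ablation to death from any cause, with patients not known to have died censored at the date last known alive. Name the first procedure explicitly, because Section 7.0 counts imaging from the first procedure and Section 9.1 from the last. The Schema allows 3 weeks for all ablation, so that choice can matter by up to 21/30.4375 = 0.7 months. State in Section 11.2 which OS summaries will be reported.

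If time from metastatic diagnosis is also reported, label it descriptive, say that it includes survival required for entry, and do not set it against the 12-month median in Section 1.1. Delayed-entry Kaplan-Meier from diagnosis is not a substitute for the ablation-origin measure.

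The cost is a protocol amendment to wording, with no new visits. Section 8.0 already lists an Ablation Form (confirm that it records the procedure date), and Section 5.10 continues survival follow-up after progression. Reported OS will be shorter by about the lead-in. Re-timing does not remove the selection of chemotherapy-stable patients with 10 or fewer treatable lesions, and the report should say so.
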